5.0 Treatment Plan

5.1 Study Drug Treatment

This study will be conducted in 2 parts, part I and Part II, as follows:

Part I:

This part will be a single-arm phase II study of rolapitant administered as single-dose on Day 1. In this part, we will estimate the preliminary efficacy of rolapitant administered on day 1 by evaluating complete response (CR) in the single arm setting.

Up to 42 patients will be enrolled in part 1 (after the amendment 4) using the Simon's Minimax 2-stage design; 24 patients will be enrolled in the first stage. If \ge 2 out of 24 patients experience CR, additional 18 patients will be enrolled. The trial will be stopped early if less than 8 patients have complete response in nausea/vomiting.

With conclusion of Part 1 of study, communication of Part 1 study results will be presented to TerSera. In addition, publication of Part 1 study results may be presented for poster abstract and/or scientific journal for publication.

The decision to move on to Part II of this study will not depend on the results of the patients who have been treated with dexamethasone at 8 mg on Days 2-5. Rather, if the first part of the trial for the patients who will be treated with dexamethasone at 12 mg on Days 2-5 was not stopped early due to lack of efficacy of rolapitant and TerSera consents to continuation of the trial, the trial will proceed to the second part of the trial.

Treatment Plan:

All patients will receive anti-emetics approximately 1- 2 hrs prior to chemotherapy infusion as follow: Dexamethasone IV daily for 5 days (12 mg on days 1-5, after the amendment 2), Ondansetron (5HT3 receptor antagonist) 16 mg IV daily for 5 days as standard of care, and Rolapitant, 180 mg will be administered PO on Day 1. For 5-days Ifosfamide regimen, the anti-emetics will be given for 6 days.

Part II: This part will be a randomized, 2-arm phase II study of rolapitant vs fosaprepitant. If the trial was not stopped early, then the trial will proceed to the second part.

Assuming 40% and 11% CR rates in Arm A, and Arm B respectively, approximately 78 evaluable subjects will be randomly assigned to receive Rolapitant or fosaprepitant (1:1) administered as a single dose. The fosaprepitant arm will be used as standard arm to prevent patient selection bias.

Treatment Plan:

Patients will be randomized into two treatment arms: Arm A/ investigational arm: single dose of rolapitant n=39. Arm B/ control arm: single dose of fosaprepitant, n=39.

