chemotherapy with Doxorubicin and Ifosfamide regimen (AI). Arm A patients will receive a single dose of rolapitant on Day 1; Arm B patients will receive a single dose of fosaprepitant on Day 1. The primary objective is to evaluate the effect of rolapitant on nausea/vomiting as compared to the effect of a single dose of fosaprepitant in cycle 1 (days 1-10). Again, a patient will be considered as to have a complete response (CR) if s/he does not experience emesis and do not need rescue medication during cycle-1 following initiation chemotherapy. The primary endpoint is CR rate in cycle 1 (days 1-10). The sample size for this part of the trial will depend on the CR rate observed in the first part of the trial. Table 1 shows sample sizes required for three presumably observed CR rates in the first part of the trial assuming that the CR rate in Arm B is 11%. For example, a total of 78 patients, 39 in each arm, will provide the study 80% power to detect the differences of CR rates between the two arms using a Fisher exact test with a 0.05 twosided significance level when the respective CR rates are 40% and 11% in Arm A, and B (15, 16). All patients that complete cycle-1 (days 1-10) of chemotherapy will be considered evaluable for the study. Patients that can't complete cycle-1 of chemotherapy due to disease progression, treatment change, withdrawal of consent, or other reasons will be replaced with new patients (maximum accrual 86 patients; 78 evaluable, potential 10% drop out rate) nQuery 7.0 was used for the sample size or power calculation.

Table 1. Sample size needed per arm in testing difference in complete response rate during cycle-1 between Arm A and B, Fisher's exact test with two-sided significance level of 0.05 and 80% power assuming the CR rate of Arm B is 11%

CR rate in Arm A	30%	40%	45%	50%
Sample size	78	39	31	24

Analysis Plans

Patients' demographic and clinical characteristics at baseline will be summarized using descriptive statistics such as mean, standard deviation, median, interquartile range (IQR), frequency where appropriate. We will apply Student t-test/Wilcoxon test and Kruskal-Wallis test/ANOVA to compare continuous variables between different patient group, and the chi-square test or the Fisher's exact test to assess the association between two categorical variables (28).

For the analysis of the primary endpoint of the first part of the trial, we will provide point estimate along with 95% exact confidence interval (CI) of CR rate.

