
For the analysis of the primary endpoint of the second part of the trial, Fisher exact test will be used to test the difference of CR rates between the two arms. CR rates along with their 95% confidence intervals (CIs) will be estimated by study arm. We will use logistic regression model (28) to assess the effect of patient specific covariates, such as treatment group, gender, etc. on the complete response. The secondary endpoints are the response rates in each of the time periods (0-24 hours, 24 hrs-120 hrs, and 120-240 hours). Logistic regression models using generalized estimating equations (GEE) will be

used to fit the response data to take the intra-patient correlation into account and to compare the differences of the response rates between the two treatment arms and to evaluate the effects of the patient specific covariates(29).

Toxicity data will be summarized by frequency tables for all patients and by treatment arm. For the efficacy endpoint, intent-to-treat analysis will be applied to the eligible patients. For the toxicity endpoint, per-treated analysis will be used to include any patient who received the treatment regardless of the eligibility nor the duration or dose of the treatment received.

If there are missing data, the reasons for missing data will be recorded, and missing-data mechanism will be checked. For data missing at random (MAR), multiple imputation techniques implemented in SAS PROC MI procedure to handle missing data will be used. For data missing not at random (MNAR), methods that add an explicit model for the missing mechanism to the data model will be applied.

The data from the patients who were treated with dexamethasone at 8 mg on Days 2-5 (prior to amendment 2) will be analyzed separately and included in relevant reports.

Randomization

Randomization will be carried out via CORe.

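### Part II's Fisher exact test is valid but leaves part of the 5% unused; Boschloo's exact test would recover some power at no cost in patients

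*Combined protocol and SAP*

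**What the plan says.** Section 11.0 uses one test both to size and to analyse Part II. Under Analysis Plans, "Fisher exact test will be used to test the difference of CR rates between the two arms". The sample-size paragraph takes 78 evaluable patients, 39 per arm, and states that this number "will provide the study 80% power to detect the differences of CR rates between the two arms". The calculation rests on a "Fisher exact test with a 0.05 twosided significance level" and on assumed CR rates of 40% for Arm A and 11% for Arm B.

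Table 1, whose caption also names Fisher's test, gives 78, 39, 31 or 24 per arm for Arm A CR rates of 30%, 40%, 45% or 50% against 11% in Arm B. The size to be used depends on the CR rate seen in Part I. Nothing in the document discusses the true size of Fisher's test or mentions an unconditional exact test.

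**The concern.** Fisher's test conditions on the total number of responders. In a trial of this size, that leaves few possible outcomes for each total, so the attainable significance levels move in coarse steps and usually fall below the nominal 5%. The sponsor accepts a 5% false-positive risk but spends less than that, and the unspent part could have bought power.

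Part II is small, so a few points of power from the choice of test alone are worth having. Only efficiency is at stake. Type I error is controlled, and the promised power is delivered.

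**Working it through.** **Inputs (Section 11.0; Section 5.1 for 1:1 allocation).** Two-sided alpha 0.05; Arm B rate 0.11; Arm A rates and sizes from Table 1; base case 39 per arm with 0.40 vs 0.11. The dropout allowance ("maximum accrual 86 patients; 78 evaluable, potential 10% drop out rate") does not enter, because the evaluable number stays at 78.

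**Formulas.** Let x and y be the responders in Arms A and B, b(·) the binomial probability, and R(x,y) = 1 if the test rejects and 0 otherwise.

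- Power = Σx Σy R(x,y) · b(x; nA, 0.40) · b(y; nB, 0.11), with Arm A's rate changed for the other scenarios.
- Size at a common rate p = the same sum with both rates equal to p. Maximum size is the largest value over a fine grid of p from near 0 to near 1.
- Fisher: R = 1 if the two-sided Fisher p-value is at most 0.05.
- Boschloo: R = 1 if the Fisher p-value is at most c, where c is the largest cut-off that keeps the maximum size at or below 0.05.

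Fisher's own maximum size is below 0.05, so c is at least 0.05. Boschloo therefore rejects whenever Fisher does and cannot have lower power.

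**Step 1: the plan's own figure.** At 39/39 and 40% vs 11%, summing over all 40 × 40 outcomes gives Fisher power 0.8024. The stated 80% reproduces.

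**Step 2: true size at 39/39.**

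| Common CR rate | Fisher | Boschloo |
|---|---|---|
| 11% | 1.8% | 3.2% |
| 25.5% | 2.8% | 4.1% |
| 40% | 2.8% | 4.8% |
| Maximum | 3.1% (at 50%) | 4.95% (at about 45%) |

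Boschloo's cut-off here is a Fisher p-value of about 0.069. As an illustration, 13/39 vs 5/39 responders (33% vs 13%) gives Fisher p = 0.058: not significant by Fisher, significant by Boschloo.

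**Step 3: equal arms at the Table 1 sizes (Arm B 11%).**

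| Per arm | Arm A rate | Fisher max size | Fisher power | Boschloo power | Gain (points) |
|---|---|---|---|---|---|
| 78 | 30% | 3.6% | 0.805 | 0.844 | 3.9 |
| 39 | 40% | 3.1% | 0.802 | 0.844 | 4.1 |
| 31 | 45% | 3.0% | 0.816 | 0.861 | 4.5 |
| 24 | 50% | 2.9% | 0.804 | 0.855 | 5.1 |

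Boschloo's maximum size is 4.8% to 4.95% at all four sizes.

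**Step 4: near-equal arms (40% vs 11%).** With exactly equal arms the Fisher p-value is unusually coarse, so the comparison was repeated for small imbalances.

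| Arm A / Arm B | Fisher max size | Gain (points) |
|---|---|---|
| 38/40 | 4.2% | 1.9 |
| 40/38 | 4.2% | 2.0 |
| 41/37 | 3.9% | 1.5 |
| 37/41 | 3.9% | 4.4 |
| 42/44 | 4.1% | 0.7 |
| 44/42 | 4.1% | 1.5 |
| 40/43 | 4.8% | 2.2 |
| 43/40 | 4.8% | 3.3 |

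The gain is also uneven across equal-arm sizes outside Table 1: 2.5 points at 38/38 and 7.2 at 35/35.

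**The case against.** The strongest reply is that nothing here is wrong. The sizing test and the analysis test agree, the 80% is delivered, the 5% limit holds, and a conditional exact test is a conventional choice. All of that stands. A reader might infer that the plan is invalid or falls short of its promised power; the reproduced 80.2% rules that out.

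The second reply is that the equal-arm figures flatter the proposal. That also stands. A reader might infer from 39/39 that Fisher's true size in this trial is 2% to 3% and that the gain is about 4 points. The document does not secure equal arms in the analysed set. The Randomization paragraph names only the system and gives no block scheme. Non-completers are replaced without a statement that the replacement joins the same arm. The efficacy analysis is intent-to-treat in eligible patients, so the analysed number need not be 78. Step 4 shows how far a small imbalance moves both figures, and even 78/78 gives a maximum size of 3.6%.

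Third, a reader might infer that Boschloo's test would rescue Part II if the true Arm A rate were near the 32% seen so far in Part I. At 39/39 and 32% vs 11%, power is 0.54 with Fisher and only 0.60 with Boschloo. Section 11.0 already handles a lower rate by re-sizing: the 78 per arm listed for 30% gives Fisher about 0.87 power at 32%.

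Fourth, the uncorrected chi-square test might seem a simpler remedy. Its maximum size at 39/39 is 5.9%, so it does not keep the 5% limit.

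What remains is that Boschloo's test dominates Fisher's at every split, by a modest and variable amount.

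**Conclusion.** The point holds as an optional gain in efficiency, not as the correction of an error. Fisher's maximum true size is 2.9% to 3.6% with equal arms at the Table 1 sizes, and 3.9% to 4.8% in the slightly unequal splits checked. Boschloo's test stays at or below 5% and adds 3.9 to 5.1 points at the four equal-arm Table 1 sizes (0.802 to 0.844 at 39/39). It adds 0.7 to 4.4 points in the near-equal splits checked, which had 37 to 44 patients per arm.

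These figures assume independent binomial outcomes, an 11% rate in Arm B and the Table 1 rates in Arm A. That Boschloo is never less powerful does not depend on those rates; the size of the gain does. A reader might also infer that the sample size could be cut, because at 40% vs 11% Boschloo reaches 0.815 at 35/35, where Fisher has 0.743. That rests on an exactly equal split that the plan does not guarantee, so it is not a sound reason to enrol fewer patients.

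**What to change.** Before any Part II outcome data are seen:

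1. In Section 11.0, Analysis Plans, name Boschloo's two-sided unconditional exact test, with size at most 0.05, as the primary Part II test, and report Fisher's test as a sensitivity result.
2. In the Part II sample-size paragraph, state that the sizes were derived for Fisher's test, whose 80% power now serves as a conservative floor.
3. Align the Table 1 caption with that statement.

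Keep the Table 1 sample sizes and the rule that re-sizes Part II from the Part I CR rate; the change of test does not replace that rule.

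The cost is small wording changes in these three places and a less familiar test. No extra patients are needed. The timing is convenient: in this version Part I is still completing its first stage (19 of 24 patients in the 12 mg dexamethasone cohort), and the Part II size has to be settled from Part I results in any case.

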7.0 Evaluation During Study

- Interim History and Physical examination including weight will be done before each cycle of chemotherapy.
- Patients will report on daily symptom record diary the adverse events, the date of all emesis episodes, intensity of nausea, and rescue medications before and during study on days 1-10 of the first cycle. Also, patients will report the functional evaluations of nausea and emesis according to Functional Living Index-Emesis (FLIE) scale in cycle 1 (e.g. days 1, 5 and 10) (26). In addition, the patients will continue to report on daily symptom record diary the adverse events while on study.
- Serum electrolytes and chemistries will be performed prior to every cycle and as frequently as needed during the cycle to monitor the toxicity
- Management of hypersensitivity to the study drug: Patients with allergic reactions can be symptomatically managed. All patients with grade 4 hypersensitivity reactions (anaphylaxis) will be removed from the study.

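### The missing-data method is selected by a MAR-or-MNAR check that observed data cannot decide, so the handling of an unconfirmed CR is left until outcomes are seen

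*Combined protocol and SAP*

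**What the plan says.** The Analysis Plans part of Section 11.0 holds the plan's only rule on missing values. It has three steps.

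- Trigger: "the reasons for missing data will be recorded, and missing-data mechanism will be checked".
- First branch: "For data missing at random (MAR), multiple imputation techniques implemented in SAS PROC MI procedure to handle missing data will be used".
- Second branch: "For data missing not at random (MNAR), methods that add an explicit model for the missing mechanism to the data model will be applied".

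It names no check, decision criterion, imputation model, pooling rule, form of MNAR model, default or sensitivity analysis.

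The primary endpoint in both parts is CR over days 1-10 of cycle 1, meaning no emesis (chemotherapy-related emesis in the Part I wording) and no rescue medication. The data come from the patient's diary. Section 7.0 says: "Patients will report on daily symptom record diary the adverse events, the date of all emesis episodes", together with nausea intensity and rescue use. No section says how a patient with blank diary days is counted for CR.

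Three other rules touch the question without settling it:

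- Section 11.0 (Part II) replaces patients who cannot complete cycle 1.
- Section 11.0 (Analysis Plans) applies intent-to-treat to eligible patients for efficacy.
- Section 9.1 makes anyone who received one dose evaluable for response.

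**The concern.** MAR and MNAR differ only in whether missingness depends on values nobody saw. Observed data can argue against missing completely at random, but cannot decide between MAR and MNAR without untestable assumptions. Recorded reasons can inform a judgement, but the plan does not say which reasons lead to which label. In practice the analyst picks the branch after seeing the outcomes and the pattern of gaps.

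The patients affected are those with missing days and no recorded failure. Anyone with a recorded qualifying emetic episode or rescue use is already a non-CR. For the rest, the branch decides whether they can be credited with a CR.

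The imputation branch also does not fit the named analyses. Part I uses a whole-number cut-off and Part II one Fisher test. Several imputed datasets give several counts and several p-values, and nothing says how to combine them. At stake is a primary result that depends on an unstated, late choice.

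**Working it through.** **The plan's own figures.** Section 11.0 states that "a total of 78 patients, 39 in each arm, will provide the study 80% power", "using a Fisher exact test with a 0.05 twosided significance level", "when the respective CR rates are 40% and 11% in Arm A, and B". Power is the sum of Bin(x; 39, 0.40) × Bin(y; 39, 0.11) over all pairs (x, y) with two-sided Fisher p ≤ 0.05. The result is 80.2%, so the stated 80% is reproduced. The Part I design in Section 11.0 (24 then 42 patients, cut-offs 2 and 8) gives a type I error of 0.036 at 11% and power of 0.951 at 32%, within its stated limits. This point disputes neither design.

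**Assumed inputs for Part II (not from the plan).** 39 per arm, 4 with unknown CR in each arm, so 35 observed per arm. Observed CRs are 14 and 4: 14/35 = 40% and 4/35 = 11.4%, close to the design rates.

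**Formula.** With m total CRs, P(x) = C(39, x) × C(39, m−x) / C(78, m). The two-sided p sums P over all tables no more probable than the one observed.

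| How the unknowns are counted | Arm A vs Arm B | p |
|---|---|---|
| Left out | 14/35 vs 4/35 | 0.0125 |
| All non-CR | 14/39 vs 4/39 | 0.014 |
| Two in Arm B as CR, the rest non-CR | 14/39 vs 6/39 | 0.068 |
| All CR in both arms | 18/39 vs 8/39 | 0.030 |
| Outer bound: all CR in A, none in B | 18/39 vs 4/39 | 0.0008 |
| Outer bound: none in A, all CR in B | 14/39 vs 8/39 | 0.21 |

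Every 39-per-arm row fits the same observed data, so no check of those data can choose among them.

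**A MAR-type completion.** Let the added CRs be I ~ Bin(4, 0.40) in Arm A and J ~ Bin(4, 0.114) in Arm B, and compute Fisher's p for (14+I)/39 vs (4+J)/39. Most of the probability of p > 0.05 comes from I=0, J=2. That is 0.6⁴ × 6 × 0.1143² × 0.8857² = 0.1296 × 0.0615 = 0.0080. All non-significant pairs together come to 0.0107, so about 99% of completions stay below 0.05. This is a simple completion, not a pooled PROC MI result.

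**Another layout.** Suppose the 4 unknowns per arm come on top of 39 observed, giving 43 per arm. With 14 vs 4 observed, all non-CR gives p=0.016 and the outer bounds are 0.001 and 0.216. With 13 vs 4, all non-CR gives 0.028 and all CR in both arms gives 0.056. A result nearer the border is more sensitive.

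**Part I.** The drug is rejected at 8 or fewer CRs among 42. Assume 7 confirmed CRs and 4 unknown. The total can then be any whole number from 7 (16.7%, rejected) to 7+4 = 11 (26.2%, not rejected). Imputing at the observed rate adds 4 × 7/38 = 0.74 on average, giving 7.74. That is not a count the cut-off or an exact interval can use directly.

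**The case against.** The text does not call for a formal test of MAR against MNAR, and a reader who infers one goes beyond it. Reasons are to be recorded, and these are information beyond the outcomes and a usual basis for judging plausible mechanisms. This stands: analysts could reach a judgement. It does not rescue the rule, because the plan never says how reasons map to a branch or what either model would be.

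A reader might take the plan's 10% as the rate of missing diaries. It is not. In Section 11.0 it is drop-out on top of the evaluable patients (78 × 1.10 = 85.8, stated as 86), and those patients are replaced. The documents give no rate of diary gaps among completers, so the 4 per arm is purely an assumption.

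A reader might also infer that choosing imputation over non-response would by itself reverse the result. The working does not support that: leaving unknowns out, counting them as non-CR, and nearly all MAR-type completions agree. The p=0.21 case needs every Arm B gap to be a CR and every Arm A gap a failure, which is an outer bound. It also runs against the plausible idea that sicker patients leave more gaps, an idea the documents do not establish.

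Replacement of non-completers reduces how often the rule is needed. But it does not cover patients who finish the cycle with diary gaps, and it sits uneasily with intent-to-treat and one-dose evaluability. Finally, Part II proceeds only if Part I succeeds and, under Section 5.1, the drug supplier consents. The same gap applies to Part I.

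**Conclusion.** The concern holds in this form. The stated selector asks the data to decide something they cannot, and no other rule fixes how an unconfirmed days 1-10 CR is counted, so the method would be chosen after outcomes are known. The imputation branch also lacks a link to the Part I cut-off and to the Part II test.

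The likely size is modest. On the assumed counts of 14 vs 4, significance is lost only under departures from MAR that differ by arm. Two Arm B unknowns counted as CR, with none in Arm A, is enough. The figures rest on an assumed 4 unknowns per arm and show sensitivity, not a forecast. They do not show that the planned analysis would give a wrong answer.

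**What to change.** Delete the mechanism check as the selector and state a fixed order for both parts.

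- **Primary:** an eligible patient in the efficacy analysis set whose days 1-10 CR cannot be confirmed counts as non-CR. This gives the whole-number count for Part I and the single Fisher test for Part II. Multiple imputation with a fully stated model could also be prespecified, but it would need a pooling rule for both.
- **Sensitivity 1:** multiple imputation under MAR, with the model (arm and observed diary days) and the pooling rule stated.
- **Sensitivity 2:** a tipping-point analysis over the imputed CR rate in each arm, varied separately.
- **Non-completers:** reconcile the replacement rule (Section 11.0, Part II) with intent-to-treat (Section 11.0, Analysis Plans) and one-dose evaluability (Section 9.1). State whether a replaced patient stays in the set as non-CR or leaves it.

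The cost is a few sentences, two extra analyses and slightly lower CR rates. If 10% of the 39 per arm were unknown (an assumption), the rates become 0.9 × 40% = 36% and 0.9 × 11% = 9.9%, and power falls from 80.2% to 73.8%. Analysing only 35 observed per arm gives 74.3%, so nearly all of that loss comes from the missing data rather than from the rule.
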